8.4 Ipilimumab

YERVOY, BMS-734016, MDX-010, anti-CTLA-4

Ipilimumab is a recombinant, human monoclonal antibody that binds to the CTLA-4. Ipilimumab is an IgG1 kappa immunoglobulin with an approximate molecular weight of 148 kDa.

Ipilimumab is produced in mammalian (Chinese hamster ovary) cell culture.

8.4.1 Supplier/How Supplied

Standard of care ipilimumab will be utilized and provided by local pharmacy. The cost of nivolumab will not be covered by the protocol. The site investigators and pharmacies will be responsible for maintenance of appropriate records and ensure appropriate supply, storage, handling, distribution, and usage of the product in accordance with the protocol and any applicable laws and regulations.

8.4.2 Preparation

Refer to current ipilimumab package insert. Ipilimumab Injection: 50 mg/10 mL (5 mg/mL) and 200 mg/40 mL (5 mg/mL) in a single-use vial.

Do not shake product.

- Inspect parenteral drug products visually for particulate matter and discoloration prior to administration. Discard vial if solution is cloudy, there is pronounced discoloration (solution may have pale-yellow color), or there is foreign particulate matter other than translucent-to-white, amorphous particles.

Preparation of Solution

- Allow the vials to stand at room temperature for approximately 5 minutes prior to preparation of infusion.
- Withdraw the required volume of ipilimumab and transfer into an intravenous bag.
- Dilute with 0.9% Sodium Chloride Injection, USP or 5% Dextrose Injection, USP to prepare a diluted solution with a final concentration ranging from 1 mg/mL to 2 mg/mL. Mix diluted solution by gentle inversion.
- Store the diluted solution for no more than 24 hours under refrigeration (2°C to 8°C, 36°F to 46°F) or at room temperature (20°C to 25°C, 68°F to 77°F).
- Discard partially used vials or empty vials of ipilimumab.

8.4.3 Storage and Stability

Store ipilimumab under refrigeration at 2°C to 8°C (36°F to 46°F). Do not freeze. Protect vials from light

8.4.5 Handling and Disposal

Ipilimumab injection is available as follows:

Carton Contents	NDC
One 50 mg vial (5 mg/mL), single-use vial	NDC 0003-2327-11
One 200 mg vial (5 mg/mL), single-use vial	NDC 0003-2328-22

Store ipilimumab under refrigeration at 2°C to 8°C (36°F to 46°F). Protect ipilimumab from light by storing in the original carton until time of use. Do not freeze or shake.

8.4.6 Administration

Administration Instructions

- Do not mix ipilimumab with, or administer as an infusion with, other medicinal products.
- Flush the intravenous line with 0.9% Sodium Chloride Injection, USP or 5% Dextrose Injection, USP after each dose.
- Administer diluted solution over 30 minutes through an intravenous line containing a sterile, non-pyrogenic, low-protein-binding in-line filter.

When administered in combination with nivolumab, infuse nivolumab first followed by Ipilimumab on the same day. Use separate infusion bags and filters for each infusion.

8.4.6 Adverse Events

Please see the package insert for a complete list of possible adverse events and guidance on adverse event management. Refer to Table 8-9 and ASCO/NCCN guidelines [18]. Also refer to section 8.5 for management guidance on potential overlapping adverse events from nivolumab, ipilimumab and cabozantinib.

Most common adverse reactions ($\geq 5\%$) with ipilimumab as a single agent are fatigue, diarrhea, pruritus, rash, and colitis. Additional common adverse reactions at the 10 mg/kg dose ($\geq 5\%$) include nausea, vomiting, headache, weight loss, pyrexia, decreased appetite, and insomnia.

Most common adverse reactions ($\geq 20\%$) with ipilimumab in combination with nivolumab are fatigue, rash, diarrhea, nausea, pyrexia, musculoskeletal pain, pruritus, abdominal pain, vomiting, cough, arthralgia, decreased appetite, dyspnea.

No dose reductions are permitted. Interrupt or slow the rate of infusion in patients with mild or moderate infusion reactions. Discontinue in patients with severe or life-threatening infusion reactions.

Grade 2 and above immune related adverse events (irAEs) may/will require drug hold/discontinuation and administration of high dose corticosteroids (0.5-2mg/kg/day of prednisone or equivalent) tapered off over a 4-6 week period. Patient are to be completely off prednisone unless used for adrenal replacement purposes prior to resuming any immunotherapy, unless discussed with the Study Chair. Additional immune modulatory agents may be required

for treatment of irAEs that are refractory to corticosteroids, such as infliximab for immune colitis and mycophenylate for immune hepatitis. Refer to guidance below in Table 8-9 and ASCO/NCCN guidelines.

During the Induction Period (Nivo-Ipi-Cabo treatment), the subject should stay on schedule and follow procedures as outlined. Drug dosing may be omitted based on toxicity guidance per protocol. If Nivolumab is restarted in the induction phase, the dose will remain at 3mg/kg for the duration of the induction phase.

During the induction phase, if an Adverse Event requires all drug to be held, and the toxicity has recovered to Grade 1 or baseline prior to the next scheduled treatment visit and the patient is eligible for Nivolumab and/or Ipilimumab, please consult study chair for approval to restart prior to the next scheduled treatment visit. If a subject is eligible to restart Nivolumab and Ipilimumab after a delay, then all subsequent visits/procedures may be shifted, including the scans, in order to complete all 4 induction cycles. The scans may be done earlier, at the investigator's discretion.

During the Maintenance phase (Nivo+Cabo treatment), starting at cycle week 13, treatment/assessment cycle date may be shifted to account for recovery from immunotherapy related toxicity. The one exception is that scans should remain every 12 weeks according to calendar days.

Table 8-9 Adverse event management for ipilimumab [Package Insert, 2018].

Target/Organ System	Adverse Reaction (CTCAE v4)	Treatment Modification
Endocrine	Symptomatic endocrinopathy	Withhold YERVOY Resume YERVOY in patients with complete or partial resolution of adverse reactions (Grade 0 to 1) and who are receiving less than 7.5 mg prednisone or equivalent per day.
	
 • Symptomatic reactions lasting 6 weeks or longer • Inability to reduce corticosteroid dose to 7.5 mg prednisone or equivalent per day 	Permanently discontinue YERVOY
Ophthalmologic	Grade 2 through 4 reactions 
 • not improving to Grade 1 within 2 weeks while receiving topical therapy or • requiring systemic treatment 	Permanently discontinue YERVOY
All Other	Grade 2	Withhold YERVOY Resume YERVOY in patients with complete or partial resolution of adverse reactions (Grade 0 to 1) and who are receiving less than 7.5 mg prednisone or equivalent per day.
	
 • Grade 2 reactions lasting 6 weeks or longer • Inability to reduce corticosteroid dose to 7.5 mg prednisone or equivalent per day • Grade 3 or 4 	Permanently discontinue YERVOY

8.5 Overlapping adverse event management guidance

Many adverse events overlap between nivolumab/ipilimumab and cabozantinib. However, the mechanisms of action of the adverse events are likely different between these two classes of therapies and they require separate management plans. For example grade 3 diarrhea attributed to ipilimumab requires drug discontinuation, a course of high dose corticosteroids and supportive care, whereas grade 3 diarrhea attributed to cabozantinib requires temporary drug hold and supportive care alone. For adverse events that are most likely to occur with one class of therapy, the adverse event management should follow for that agent. An example is a grade 3-4 electrolyte abnormality, which is more common with cabozantinib. In this case, all three drugs should be temporarily held, but no corticosteroids given as this is likely not an immune related event. However, in patients with life threatening events (grade 4) or no improvement with drug hold after 5 days, then corticosteroids should be considered as it may be a rare irAE. In situations where a grade 3-4 adverse event could be due to either class of therapy, all drugs will need to be held and high dose corticosteroids administered if recommended by standard nivolumab or ipilimumab guidelines. After recovery of adverse event to grade 1 or baseline, cabozantinib can be reinitiated even if the corticosteroid taper has not been completed. The cabozantinib may need to be dose reduced if indicated by the included dosing guidelines. For some situations, such as grade 2 elevated transaminase levels, it may be appropriate to hold all study drugs, but monitor for improvement prior initiation of corticosteroids. In patients where nivolumab/ipilimumab or nivolumab cannot be restarted, cabozantinib would continue alone as outlined in the protocol treatment schema unless permanent discontinuation indicated (section 8.2). Similarly, in patients where cabozantinib cannot be restarted, nivolumab/ipilimumab or nivolumab alone may be continued as outlined in the protocol treatment schema if not meeting discontinuation rules and adverse event(s) has recovered to grade 1 or baseline and patient has successfully tapered of corticosteroids (and other immune modulatory agents). An exception is grade 2 endocrine disorders that can be treated with hormone replacement. When it is unclear how to manage the adverse event, hold drugs and consult the principal investigator.

During the Induction Period (Nivo-Ipi-Cabo treatment), the subject should stay on schedule and follow procedures as outlined. Drug dosing may be omitted based on toxicity guidance per protocol. If Nivolumab is restarted in the induction phase, the dose will remain at 3mg/kg for the duration of the induction phase.

During the induction phase, if an Adverse Event requires all drug to be held, and the toxicity has recovered to Grade 1 or baseline prior to the next scheduled treatment visit and the patient is eligible for Nivolumab and/or Ipilimumab, please consult study chair for approval to restart prior to the next scheduled treatment visit. If a subject is eligible to restart Nivolumab and Ipilimumab after a delay, then all subsequent visits/procedures may be shifted, including the scans, in order to complete all 4 induction cycles. The scans may be done earlier, at the investigator's discretion.

During the Maintenance phase (Nivo+Cabo treatment), starting at cycle week 13, treatment/assessment cycle date may be shifted to account for recovery from immunotherapy related toxicity. The one exception is that scans should remain every 12 weeks according to calendar days.

Management of Hepatocellular Toxicity Associated with Cabozantinib and Nivolumab/Ipilimumab or Nivolumab

Elevations of aminotransferases (ALT and AST) and bilirubin have been observed during treatment with cabozantinib. It is recommended that subjects with elevation of ALT, AST, and/or bilirubin have more frequent laboratory monitoring of these parameters. If possible, hepatotoxic concomitant medications should be discontinued in subjects who develop increased values of ALT, AST, or bilirubin, and other causes (eg, cancer-related, infection) should be evaluated.

The following conditions require discontinuation of cabozantinib:

- Drug-related ALT or AST $> 3 \times$ ULN in combination with total bilirubin $> 2 \times$ ULN without reasonable other explanation, consistent with drug-induced liver injury (DILI).
- Drug-related ALT or AST $> 8 \times$ ULN.

Elevations of aminotransferases when hepatic metastases are present may not require dose modifications if there are no progressive changes in the aminotransferases (less than a doubling) and if there are no progressive elevations in serum bilirubin concentration or coagulation factors. [Table 8-108-10](#) provides suggested guidance on management of hepatotoxicity related to cabozantinib and/or nivolumab/ipilimumab or nivolumab. However, if Grade 2 or higher abnormalities of both a serum transaminase (ALT and/or AST) and serum bilirubin are documented, all study treatment must be discontinued. Dose holds should not alter the timing of other study assessments, including but not limited to tumor imaging scheduled based on W1D1 (≤ 3 days after start of treatment).

Table 8-10: Management of Hepatotoxicity Associated with Study Treatment

Severity of LFT Elevations by CTCAE v4	Dose Modification Guidance	Management/Follow-up Guidance
Grade 1 AST or ALT $>$ ULN to $3.0 \times$ ULN and/or total bili $>$ ULN to $1.5 \times$ ULN	
 • Cabozantinib: 
 – Continue cabozantinib per protocol • Nivolumab/Ipilimumab or Nivolumab: 
 – Continue therapy per protocol 	
 • Monitor LFTs per protocol • Discontinue concomitant hepatotoxic medications, if possible


Grade 2 AST or ALT > 3.0 x ULN to ≤ 5 x ULN or total bili > 1.5 x ULN to ≤ 3 x ULN
	
 • Cabozantinib: 
 – Interrupt cabozantinib dosing. – If LFTs return to baseline grade, resume cabozantinib at a reduced dose. • Nivolumab/Ipilimumab or Nivolumab: 
 – Hold therapy per protocol. – If LFTs return to baseline grade, resume therapy per protocol 	
 • Monitor LFTs twice weekly or more frequently as deemed clinically necessary. • If tapering off steroid therapy, monitor LFTs once weekly or more often per clinical judgment • If LFTs return to baseline grade, resume with routine monitoring • If LFT elevations persist > 7 days or worsen: 
 – Administer 0.5-1 mg/kg/day methylprednisolone or oral equivalent – When LFTs return to baseline grade or CTCAE Grade ≤1, taper steroids over at least 4 weeks – Add prophylactic antibiotics for opportunistic infections if on immune suppression > 1 month or prior to 1 month per investigator decision.

Grade 3-4 AST or ALT > 5 x ULN or total bili > 3 x ULN or as otherwise specified
	
 • Cabozantinib: 
 – Discontinue cabozantinib if: 
 1) ALT or AST > 3 × ULN AND total bilirubin > 2 × ULN AND no radiographic evidence of biliary obstruction, or 2) ALT or AST > 8 x ULN. – Otherwise interrupt cabozantinib dosing and resume at a reduced dose after LFTs return to baseline grade (Study Principal Investigator approval required) • Nivolumab /Ipilimumab or Nivolumab: 
 – Discontinue combination or monotherapy therapy – Exception: Can resume nivolumab after LFTs return to baseline grade if grade 3 event occurred while receiving Nivolumab/Ipilimumab (Study Principal Investigator approval required) 	
 • Monitor LFTs twice weekly or more frequently as deemed clinically necessary • During steroid taper, monitor LFTs once weekly or more often per clinical judgment • For Grade 3: 
 – Administer 1.0-2.0 mg/kg/day methylprednisolone IV or PO equivalent • For Grade 4: 
 – Administer 2.0 mg/kg/day methylprednisolone IV • Add prophylactic antibiotics for opportunistic infections if on immune suppression > 1 month or prior to 1 month per investigator decision. • When LFTs return to baseline grade or Grade 2, convert to oral prednisone (if not already on it) and taper steroids over at least 4 weeks • If LFT elevations do not improve in > 3-5 days, worsen or rebound: 
 – Add mycophenolate mofetil 1g BID – If no response within an additional 3-5 days, consider other immune-suppressants per local guidelines and hepatology consultation. Taper off steroid first over at least 4 weeks and then taper off mycophenolate (decrease total 24hr dose by 500mg after every 7 days).

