6.0 INCLUSION/EXCLUSION CRITERIA

To be eligible for the study the subject must meet all of the inclusion and none of the exclusion criteria:

Inclusion Criteria

1. All patients must have unresectable stage IIIb-IIIId or IV melanoma by AJCC 8th edition.
Note: Patients with uveal melanoma are excluded from this study.
2. Age \geq 18 and ECOG Performance Status of 0 or 1.
3. Measurable disease by imRECIST.
4. Baseline tumor specimen available – either archived tumor specimen collection within the past year and no intervening treatment or fresh tumor collection (A waiver may be considered for the baseline biopsy requirement after discussion with study principal investigator).
5. Recovery to baseline or \leq Grade 1 CTCAE v4 from toxicities related to any prior treatments, unless AE(s) are clinically nonsignificant and/or stable on supportive therapy.
6. Adequate organ and marrow function, based upon meeting all of the following laboratory criteria within 14 days before first dose of study treatment:
 - a. Absolute neutrophil count (ANC) \geq 1500/mm³ (\geq 1.5 GI/L) without granulocyte colony-stimulating factor support.
 - b. White blood cell count \geq 2500/mm³ (\geq 2.5 GI/L).
 - c. Platelets \geq 100,000/mm³ (\geq 100 GI/L) without transfusion.
 - d. Hemoglobin \geq 9 g/dL (\geq 90 g/L).
 - e. Alanine aminotransferase (ALT), aspartate aminotransferase (AST), and alkaline phosphatase (ALP) \leq 3 \times upper limit of normal (ULN). ALP \leq 5 \times ULN with documented bone metastases.
 - f. Total bilirubin \leq 1.5 \times ULN (for subjects with Gilbert's disease \leq 3 \times ULN).
 - g. Serum albumin \geq 2.8 g/dl.
 - h. Serum creatinine \leq 2.0 \times ULN or calculated creatinine clearance \geq 30 mL/min (\geq 0.5 mL/sec) using the Cockcroft-Gault equation:
Males: $(140 - \text{age}) \times \text{weight (kg)} / (\text{serum creatinine [mg/dL]} \times 72)$
Females: $[(140 - \text{age}) \times \text{weight (kg)} / (\text{serum creatinine [mg/dL]} \times 72)] \times 0.85$
 - i. Urine protein/creatinine ratio (UPCR) \leq 1 mg/mg (\leq 113.2 mg/mmol).
7. Capable of understanding and complying with the protocol requirements and must have signed the informed consent document.

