8.2.4.1.11 Hepatocellular Toxicity

Elevation of aminotransferases (ALT and AST): Evaluation of subjects with elevated transaminases or bilirubin should be individualized and guided by the presence of specific risk factors such as liver conditions (eg, liver cirrhosis, metastases to the liver, thrombosis of portal or hepatic vein, hepatocellular carcinoma, hepatitis), concomitant hepatotoxic medication, alcohol consumption, and cancer related causes.

As immune hepatitis has been observed with nivolumab and ipilimumab, management beyond cabozantinib drug hold may be necessary. If ALT or AST elevations are grade 2 or greater, immune checkpoint therapy may need to be held/discontinued and patient initiated on corticosteroids. Refer to specific guidance in section 8.5 for management of liver toxicity suspected to be potentially from cabozantinib and immune checkpoint therapy.

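### The all-drug liver stop in section 8.5 has no exception for the unchanged bilirubin of Gilbert's subjects whom inclusion 6f admits at >1.5 to 3 × ULN

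*Combined protocol and SAP*

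**What the plan says.** **Entry (section 6.0).** Inclusion 6f limits total bilirubin to 1.5 × ULN, with a separate limit of 3 × ULN "for subjects with Gilbert's disease". Inclusion 6e limits ALT and AST to 3 × ULN.

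**Grading (section 8.5, Table 8-10).** The Grade 2 row covers ALT or AST of >3 to 5 × ULN, or "total bili > 1.5 x ULN to ≤ 3 x ULN". Limits are multiples of ULN, not of the subject's baseline. The row interrupts cabozantinib and holds the checkpoint inhibitors. For the latter it says "If LFTs return to baseline grade, resume therapy per protocol"; cabozantinib resumes at a reduced dose.

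**Mandatory stop (section 8.5, text before Table 8-10).** The table is introduced as suggested guidance. The next sentence overrides it: "if Grade 2 or higher abnormalities of both a serum transaminase (ALT and/or AST) and serum bilirubin are documented, all study treatment must be discontinued".

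**Neighbouring rules.** The cabozantinib-only stop earlier in section 8.5 (drug-related ALT or AST >3 × ULN with bilirubin >2 × ULN) applies only "without reasonable other explanation, consistent with drug-induced liver injury (DILI". The Grade 3-4 row of Table 8-10 repeats those thresholds for cabozantinib, but its only let-out is in the words "AND no radiographic evidence of biliary obstruction". Table 8-8 (section 8.3.6) withholds nivolumab for bilirubin above 1.5 and up to 3 × ULN.

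**The concern.** The plan deliberately admits a group whose bilirubin may already be Grade 2 on the trial's own scale, then uses Grade 2 bilirubin as one of two triggers for stopping everything. In these subjects the bilirubin trigger is met on the day they enter, so the two-part rule becomes a one-part rule: a new Grade 2 ALT or AST is enough. Section 8.5 uses hold or interrupt for temporary measures and discontinue for ending a drug, so the difference is between a pause and the end of protocol therapy.

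At stake is a mandatory dosing rule for individual subjects. A benign, unchanged laboratory value would turn a recoverable transaminase rise into the loss of all study treatment.

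**Working it through.** The plan states no figure on this point, so the check is to apply its limits to the same values.

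**1. The bands coincide.** Inclusion 6f for Gilbert's disease only: above 1.5, up to 3 × ULN. Table 8-10 Grade 2 bilirubin: above 1.5, up to 3 × ULN. The whole extra band is Grade 2.

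**2. Any Grade 2 transaminase is new.** Entry ALT and AST are at most 3 × ULN and Grade 2 starts above 3 × ULN, so nobody should enter with it.

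**3. Applying the rules** (values in × ULN):

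| Bilirubin | ALT or AST | Bilirubin grade | ALT/AST grade | All-drug stop | Cabozantinib-only limits (ALT/AST >3, bilirubin >2) |
|---|---|---|---|---|---|
| 1.5 | 3.1 | 1 | 2 | No; hold and resume | Not met |
| 1.5 | 5.0 | 1 | 2 | No; hold and resume | Not met |
| 1.6 | 3.0 | 2 | 1 | No | Not met |
| 1.6 | 3.1 | 2 | 2 | Yes | Not met |
| 2.0 | 5.0 | 2 | 2 | Yes | Not met |
| 2.1 | 3.1 | 2 | 2 | Yes | Met |
| 3.0 | 5.0 | 2 | 2 | Yes | Met |

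Two subjects with the same ALT of 3.1 × ULN are treated differently because one has a bilirubin of 1.6 and the other 1.5, even if neither bilirubin has changed since screening.

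**4. Bilirubin alone.** The third row has no Grade 2 transaminase, yet bilirubin of 1.6 meets the Table 8-10 Grade 2 row, which is joined by an or, and the Table 8-8 withhold row. On a literal reading such a subject meets a hold criterion from the first on-study draw. Table 8-10 softens this by resuming at baseline grade. Table 8-8 resumes only at Grade 0 or 1, which a stable bilirubin in the band never reaches.

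**5. The pair will be seen together.** Under Table 7-1, footnote 2, the Day 1 and Day 8 laboratory panels both include ALT, AST and total bilirubin.

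**6. The existing qualifier does not help.** Every case with ALT or AST >3 and bilirubin >2 × ULN also has bilirubin >1.5 × ULN, so it also meets the all-drug stop. The other-explanation qualifier on the cabozantinib-only rule therefore cannot keep a subject on cabozantinib.

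**7. Size.** Two inputs would be needed, and neither is given.
- The number of Gilbert's subjects with baseline bilirubin above 1.5 × ULN, out of up to 27, is not stated, and no prevalence is cited.
- The Grade 2 ALT/AST rate on the triplet is not stated. Table 3-4 (n = 18) gives ALT as 10 of any grade and 2 of Grade 3-4. Grade 2 alone could be anything from 0 to (10 − 2)/18 = 44%, or (11 − 2)/18 = 50% if the printed 61% (11/18) is right rather than the count of 10. AST is listed separately (8 of any grade, 1 of Grade 3-4), and the number with either is not printed.

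**The case against.** **The literal reading can be contested.** The stop sits under a heading about hepatotoxicity associated with study drugs. Section 8.2.4.1.11 says that evaluation of raised transaminases or bilirubin "should be individualized and guided by the presence of specific risk factors such as liver conditions". Section 10.1.1 has pre-existing conditions recorded as adverse events if they worsen, and section 8.5 sends unclear cases to the principal investigator. A sensible investigator might spare the subject. That is fair as a forecast of behaviour, but none of these is an exemption. The ALT rise can be drug-related while the bilirubin is not, and the stop does not test the bilirubin half separately. Section 8.2.4.1.11 itself refers the reader to section 8.5. The stop is not unclear; it is clear and unsuited to this group. The relief for hepatic metastases concerns a different condition and comes before the overriding sentence.

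**A strict combined stop is a defensible safety choice on this triplet.** This stands, and it limits the remedy. Importing a general other-explanation clause into the all-drug stop would relax it for every subject and for causes such as metastases or infection.

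**Stronger readings the documents do not support.** A reader might infer that all three drugs are always lost; that holds only in the 12-week induction, because ipilimumab is not given afterwards. A reader might use Table 3-4 to project a sizeable number affected. But its Grade 3-4 rate (2/18 = 11%) is not a floor for this harm, since at that grade Table 8-10 already discontinues the checkpoint inhibitors for anyone, with limited resumption on approval. Its any-grade ALT rate is not a ceiling, since AST also triggers the rule.

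**Conclusion.** The conflict is in the text, and it is minor. A subject with Gilbert's disease and stable bilirubin of >1.5 to 3 × ULN loses all study treatment on a new ALT or AST of >3 to 5 × ULN, where a subject with bilirubin at or below 1.5 × ULN holds and resumes. The same bilirubin with normal transaminases also meets two hold rows.

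This rests on reading the mandatory sentence as written, and it applies only while bilirubin is actually above 1.5 × ULN. The number affected cannot be estimated; it is few, possibly none, of up to 27. A reader might infer that the primary result is at risk. The documents do not support that: the one-year PFS analysis, the decision rule and the sample size are unchanged.

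**What to change.** Add one sentence to section 8.5: *In subjects with known Gilbert's disease, total bilirubin that is at most 3 × ULN and not above the subject's baseline value does not by itself count as a Grade 2 bilirubin abnormality.* State that it applies to the all-drug stop, to the bilirubin limbs of Table 8-10 (including the cabozantinib stop in the Grade 3-4 row) and to the bilirubin limb of the Table 8-8 non-HCC hepatitis withhold row. Say which pre-dose value is the baseline, since Table 7-1 schedules laboratory tests at both screening and Day 1.

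With this change, stable bilirubin of 1.8 × ULN with a new ALT of 4 × ULN follows the Grade 2 row: all drugs held, and "Monitor LFTs twice weekly or more frequently as deemed clinically necessary". If bilirubin rises from 1.8 to 2.4 × ULN with the same ALT, the stop still applies. Bilirubin above 3 × ULN is never excused.

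Do not add a general other-explanation clause to the all-drug stop.

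The cost is a short wording amendment, with no new tests and no eligibility change; inclusion 6f already requires a baseline bilirubin. The downside is that true liver injury in a Gilbert's subject might be stopped slightly later, which the hold and the closer monitoring limit.

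### The grade 3-4 row of Table 8-10 allows restarts that the overriding Section 8.5 sentence rules out when transaminase and bilirubin are both grade 2 or higher

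*Combined protocol and SAP*

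**What the plan says.** The hepatotoxicity part of Section 8.5, with Section 8.3.6, contains four statements that bear on a subject whose transaminase and bilirubin are both raised.

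- **The override sentence, just above Table 8-10.** The text says the table "provides suggested guidance on management of hepatotoxicity related to cabozantinib and/or nivolumab/ipilimumab or nivolumab. However, if Grade 2 or higher abnormalities" and goes on to require a full stop: "Grade 2 or higher abnormalities of both a serum transaminase (ALT and/or AST) and serum bilirubin are documented, all study treatment must be discontinued". It gives no higher bilirubin threshold, no exemption and no restart.
- **The cabozantinib bullets earlier in Section 8.5.** Cabozantinib must stop for drug-related ALT/AST above 3 x with bilirubin above 2 x ULN and no other reasonable cause, or for drug-related ALT/AST above 8 x ULN.
- **Table 8-10, grade 3-4 row** (ALT/AST above 5 x or bilirubin above 3 x ULN, or as specified elsewhere). Cabozantinib stops if ALT/AST is above 3 x and bilirubin above 2 x ULN "AND no radiographic evidence of biliary obstruction", or if ALT/AST is above 8 x ULN. In other cases: "Otherwise interrupt cabozantinib dosing and resume at a reduced dose after LFTs return to baseline grade (Study Principal Investigator approval required". Nivolumab or the combination stops, with one exception: "Can resume nivolumab after LFTs return to baseline grade if grade 3 event occurred while receiving Nivolumab/Ipilimumab (Study Principal Investigator approval required".
- **Section 8.3.6.** Maintenance nivolumab is allowed after recovery from an immune-related event in induction that was most likely due to ipilimumab, with hepatitis given as an example, if the subject is benefiting.

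The grade 2 row of Table 8-10 is entered at ALT/AST above 3 to 5 x "ULN or total bili > 1.5 x ULN" (up to 3 x ULN). It says of cabozantinib: "If LFTs return to baseline grade, resume cabozantinib at a reduced dose". It lets the immunotherapy resume on the same condition.

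**The concern.** The sentence and the grade 3-4 row both address combined transaminase and bilirubin elevation, but they differ in threshold (1.5 against 2 x ULN), in exemption (none against biliary obstruction) and in the drugs covered (all against cabozantinib only). If the sentence governs, the row's threshold and its obstruction exemption can never decide a case. Either the table holds dead text or the sentence is broader than its authors meant.

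The stake is rechallenge. The Section 8.5 bullets themselves link combined elevation to drug-induced liver injury. A site working from the table row could restart a drug in a subject for whom the sentence requires discontinuation.

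**Working it through.** There is no sample-size or power figure to reproduce. The check is to write the rules as conditions and compare them.

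**Inputs** (all x ULN; grades as printed in Table 8-10): grade 2 starts at ALT/AST >3 and at bilirubin >1.5.

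- Sentence: stop all drugs if ALT/AST >3 and bilirubin >1.5.
- Grade 3-4 row applies if ALT/AST >5 or bilirubin >3.
- Cabozantinib in that row: discontinue if (ALT/AST >3, bilirubin >2, no obstruction) or ALT/AST >8; otherwise interrupt, then resume at a reduced dose with approval.
- Nivolumab in that row: discontinue, except that it may resume with approval after a grade 3 event on nivolumab/ipilimumab. Bilirubin is not mentioned.

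**Test points for cabozantinib**

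| ALT/AST | Bilirubin | Obstruction | Sentence | Grade 3-4 row | Result |
|---|---|---|---|---|---|
| 6 | 1.0 | either | does not apply | may resume | no conflict |
| 6 | 1.8 | either | stop all | may resume | conflict |
| 6 | 2.5 | no | stop all | discontinue | agree |
| 6 | 2.5 | yes | stop all | may resume | conflict |
| 4 | 3.5 | no | stop all | discontinue | agree |
| 4 | 3.5 | yes | stop all | may resume | conflict |
| 9 | 1.8, 2.5 or 3.5 | either | stop all | discontinue | agree |

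**Ranges.** Among subjects with both tests at grade 2 or higher, sentence and row differ on cabozantinib in these ranges:

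1. ALT/AST >5 to 8 with bilirubin >1.5 to 2, with or without obstruction.
2. Bilirubin >2 with obstruction, where the row applies and ALT/AST is not above 8. That is ALT/AST >5 to 8 with bilirubin >2, or ALT/AST >3 to 5 with bilirubin >3.

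In the rest of that group within the row they agree: ALT/AST >8, or bilirubin >2 without obstruction.

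**Nivolumab.** They differ wherever both tests are at grade 2 or higher and the event was grade 3 on nivolumab/ipilimumab. At ALT 6 and bilirubin 2.5 without obstruction, for example, the row stops cabozantinib but leaves the nivolumab exception open. Section 8.3.6 points the same way for hepatitis attributed to ipilimumab.

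**The bullets as a third rule.** At ALT 6 and bilirubin 1.8 they do not require cabozantinib to stop, because bilirubin is not above 2. At ALT 6 and bilirubin 2.5 they do, if the elevation is drug-related and otherwise unexplained. They say nothing about nivolumab or ipilimumab.

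**Grade 2 row.** Read alone, ALT 4 with bilirubin 1.8 would allow all drugs to resume. The grade 1 row says "ULN and/or total bili" where the grade 2 row has only an 'or', so the grade 2 row can be read as meaning one abnormal test. It does not say so.

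**The case against.** The strongest reply is that the protocol already ranks its rules. The table is offered as suggestion, and the next sentence overrides it in mandatory terms. That stands: a reader might infer that sites are left to choose between two equal instructions, and the documents do not support this. The ranking does not repair the row, however. The row cannot be confined to isolated elevation, because its first cabozantinib criterion is itself a combined rule.

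Second, obstruction may be another explanation that takes the case outside drug-related hepatotoxicity, which is the subject of this part of Section 8.5. That is a fair reading, although the sentence carries no such qualifier. The obstruction range is therefore arguable. The range at bilirubin >1.5 to 2 x ULN does not depend on obstruction.

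Third, there are safeguards. Both grade 3-4 restarts need principal investigator approval. Section 8.5 tells sites to hold drugs and consult when management is unclear, and asks for study chair approval of certain early restarts in induction. Table 8-8 permanently stops nivolumab at ALT/AST above 5 x or bilirubin above 3 x ULN, and Table 8-9 permanently stops ipilimumab at grade 3 or 4. These limit the risk but do not remove it. Approval names who decides without saying which rule to apply. A reader of the row alone sees no uncertainty to raise. The Table 8-10 exception and Section 8.3.6 both depart from Table 8-8 for nivolumab. The grade 2 row has no principal investigator approval step.

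Fourth, the sentence says discontinued, whereas Tables 8-8 and 8-9 say permanently discontinue. If a later restart were allowed under the sentence, much of the conflict would go. The grade 3-4 row itself sets discontinuing cabozantinib against interrupting and resuming it, so a stop without restart is the more natural meaning.

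**Conclusion.** The inconsistency is real and narrow. It concerns only subjects with both tests at grade 2 or higher. Within that group it covers cabozantinib at ALT/AST >5 to 8 x with bilirubin >1.5 to 2 x ULN; arguably cabozantinib with biliary obstruction at bilirubin >2 x ULN, where the row applies and ALT/AST is not above 8 x ULN; and nivolumab after a grade 3 event on the combination.

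A reader might infer that the whole grade 3-4 row contradicts the text, or that the grade 2 row certainly does. Neither follows: the sentence does not apply when only one test is abnormal, and the grade 2 row admits an isolated-elevation reading. The ranges describe the rules and say nothing about how often subjects would fall in them.

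The conclusion rests on the grades printed in Table 8-10 and on reading discontinued as excluding restart. Severity is low. The primary analysis, sample size and power are unaffected.

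**What to change.** Ask the investigators which combined rule they intend, then align the text.

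- **If the Section 8.5 sentence stands:** state in Table 8-10 that the grade 2 row covers isolated elevation only. State also that the grade 3-4 restart options (the residual cabozantinib case and the nivolumab exception) do not apply when transaminase and bilirubin are both grade 2 or higher, in which case the Section 8.5 stop governs. Bring the cabozantinib bullet in Section 8.5 and the maintenance-nivolumab allowance in Section 8.3.6 into line.
- **If the rule above 2 x ULN without obstruction is intended:** amend the Section 8.5 sentence to match the bullet and the grade 3-4 row.

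The cost is one question and wording changes: notes in two table rows plus two short alignments, or one amended sentence. No visit, test or analysis changes.
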